8.2. Schedule of Visits and Assessments

The schedule of visits and assessments is shown in [Table 2](#) for screening through the treatment period, and in [Table 3](#) for the safety follow-up period.

For a missed visit, the site should attempt to contact the subject to reschedule.

Subjects who discontinue from the study prematurely will be encouraged to return for an early termination (ET) visit and to participate in a subsequent follow-up period. The Visit 14 assessments will serve as early termination assessments for any subject who withdraws prior to completion. The safety follow-up period for subjects who discontinue early should mirror the visits displayed in [Table 3](#).

Table 2: Schedule of Visits and Assessments, Screening and Treatment Period

Evaluation	Screening ^a	ALKS 5461 Treatment Period												
		Base-line	Week 1	Week 2	Week 4	Week 6	Week 8	Week 14	Week 20	Week 26	Week 32	Week 38	Week 44	Week 52
Study Day:	-28 to -1	1	8 (±1)	15 (±1)	29 (±3)	43 (±3)	57 (±3)	99 (±3)	141 (±3)	183 (±3)	225 (±3)	267 (±3)	309 (±3)	ET/365 ^b (±3)
Visit Number:	1	2 ^c	3	4	5	6	7	8	9	10	11	12	13	14
Informed Consent ^d	X													
Qualification/ Diagnostic Assessments														
Eligibility Criteria Review	X	X ^e												
Demographics	X													
Medical/ Psychiatric History	X	X ^e												
Serology Testing ^f	X													
ATRQ	X													
MINI	X													
Breath Alcohol Test ^g	X													
Height	X													
Full Physical Examination	X													
HAM-D	X	X ^e												
Qualification/ Safety Assessments														
Weight/ Vital Signs ^h	X	X ^e	X	X	X	X	X	X	X	X	X	X	X	X
12-lead ECG	X	X ^e	X							X				X
Drug Screening ⁱ	X	X ^e	X					X		X		X		X
Pregnancy Testing ^j	X	X ^e						X		X		X		X
Symptom-Directed Physical Examination		X												X

Table 2: Schedule of Visits and Assessments, Screening and Treatment Period (Continued)

Evaluation	Screening ^a	ALKS 5461 Treatment Period												
		Base-line	Week 1	Week 2	Week 4	Week 6	Week 8	Week 14	Week 20	Week 26	Week 32	Week 38	Week 44	Week 52
Study Day:	-28 to -1	1	8 (±1)	15 (±1)	29 (±3)	43 (±3)	57 (±3)	99 (±3)	141 (±3)	183 (±3)	225 (±3)	267 (±3)	309 (±3)	ET/365 ^b (±3)
Visit Number:	1	2 ^c	3	4	5	6	7	8	9	10	11	12	13	14
Blood and Urine Samples for Safety Labs	X	X ^c	X					X		X		X		X
C-SSRS ^k	X	X ^c	X	X	X	X	X	X	X	X	X	X	X	X
COWS ^l														X
Adverse Event Monitoring	X	X	X	X	X	X	X	X	X	X	X	X	X	X
Concomitant Medication Review ^m	X	X	X	X	X	X	X	X	X	X	X	X	X	X
Illicit Substances Review ⁿ	X	X	X	X	X	X	X	X	X	X	X	X	X	X
Exploratory Efficacy Assessments														
HAM-A		X ^c			X		X	X		X		X		X
CGI-S		X ^c	X	X	X	X	X	X	X	X	X	X	X	X
MADRS ^o	X	X ^c	X	X	X	X	X	X	X	X	X	X	X	X
Additional Study Procedures														
Dispense Study Drug ^p		X	X	X	X	X	X	X	X	X	X	X	X	X
Study Drug Adherence Review ^q			X	X	X	X	X	X	X	X	X	X	X	X
ADT Adherence Review ^r		X	X	X	X	X	X	X	X	X	X	X	X	X
Blood sample – PK ^s			X	X	X	X	X	X	X	X	X	X	X	X
Emergency Treatment Card ^t		X	X	X	X	X	X	X	X	X	X	X	X	X

ADT=antidepressant therapy; ATRQ=Massachusetts General Hospital Antidepressant Treatment Questionnaire; CGI-S=Clinical Global Improvement – Severity; COWS=clinical opiate withdrawal scale; C-SSRS=Columbia Suicide Severity Rating Scale; ECG=electrocardiogram; ET=early termination; HAM-A=Hamilton Rating Scale for Anxiety; HAM-D=17-item Hamilton Rating Scale for Depression; MADRS=Montgomery-Åsberg Depression Rating Scale; MINI=Mini International Neuropsychiatric Interview; PK=pharmacokinetic.

- ^a Only New Subjects will participate in the screening visit. Screening may be repeated in some cases for Potential New Subjects, but only after approval by the medical monitor
- ^b Visit 14/ET should occur within 24 hours of the subject's last dose of ALKS 5461
- ^c For Continuing Subjects and Lead-in Subjects, identical assessments taken at the subject's Visit 2 of the antecedent study for Lead in Subjects and last treatment visit of the antecedent study for continuing subjects do not need to be repeated at Visit 2 unless more than 10 days elapses between these visits. If more than 10 days elapses between visits, all assessments must be performed at Visit 2 (ie data cannot be carried forward).
- ^d Eligible, consenting New Subjects will give written consent at the screening visit. Eligible, consenting Continuing Subjects and Lead-in Subjects will give written consent prior to participating in any study-specific procedures on Visit 2
- ^e To be conducted predose on Visit 2
- ^f For hepatitis B surface antigen, anti-hepatitis C antibodies, and human immunodeficiency virus
- ^g Breath alcohol test may be repeated for any participating subject at any point during the study based on investigator's judgment
- ^h Vital sign measurements include oral temperature, respiratory rate, blood pressure, and heart rate. Blood pressure, respiratory rate, and heart rate will be measured after the subject has been in a supine position for at least 5 minutes
- ⁱ Centralized drug screen testing at screening, local drug screen testing (via dipstick) for all other time points. The urine drug screen at Visit 1 may be repeated based on investigator judgment. The test can also be repeated at any time during the study, should the investigator feel it is warranted
- ^j Serum pregnancy testing at screening; urine pregnancy testing at all other visits
- ^k At screening the "Baseline" version of the C-SSRS will be administered and at all other visits the "Since Last Visit" version will be administered
- ^l COWS to be administered by a medical professional
- ^m All medications (prescription and non-prescription, including vitamins and herbal supplements) including ADT taken within 30 days will be recorded at screening. Any changes will be recorded at subsequent visits
- ⁿ Subject will be queried at screening on illicit substances used within 30 days, with updates made at each subsequent visit
Note: additional dispensation visits may be required based on country specific regulatory requirements. No other activities or assessments are done on these days.
- ^o The MADRS should be administered prior to the HAM-D, CGI-S and HAM-A on visits when multiple assessments are scheduled
- ^p First dose of ALKS 5461 (at Visit 2) to be administered on-site; ALKS 5461 to be dispensed at each indicated visit for subjects to self-administer starting on Day 2. Self-administration should be recommended to occur at bedtime
- ^q Via pill count and subject query
- ^r Via subject query
- ^s One PK blood sample will be collected during each indicated visit from consenting subjects enrolled in the United States only. When PK and safety blood samples are scheduled to be collected on the same day, efforts should be made to collect both samples during the same draw.
- ^t Dispense card on Visit 2; confirm possession of card at each subsequent visit and re-dispense if necessary

Table 3: Schedule of Assessments, Safety Follow-up Period

Evaluation	Safety Follow-up Period										
	1 (+1)	2 (+1)	3 (+1)	4 (+1)	5 (+1)	6 (+1)	7 (+1)	10 (+2)	14 (±2)	21 (+2)	28 (±2)
Days post end of treatment:	366	367	368	369	370	371	372	375 (+2)	379 (±2)	386 (+2)	393 (±2)
Study Day:	366	367	368	369	370	371	372	375 (+2)	379 (±2)	386 (+2)	393 (±2)
Visit ^a	15	Phone	Phone	Phone	Phone	Phone	16	Phone	17	Phone	18
Adverse Event Monitoring ^b	X	X	X	X	X	X	X	X	X	X	X
Concomitant Med Review ^c	X	X	X	X	X	X	X	X	X	X	X
Illicit Substances Review ^c	X						X		X		X
Emergency Treatment Card ^d	X						X		X		X
ADT Adherence Review ^e	X						X		X		X
Brief Symptom-Directed Physical Exam	X						X		X		X
Weight/ Vital Signs ^f	X						X		X		X
C-SSRS ^g	X						X		X		X
Drug Screen ^h	X						X		X		X
COWS ⁱ	X						X		X		X
12-Lead ECG											X
Blood and Urine Samples for Safety Labs											X
CGI-S							X		X		X

ADT=antidepressant therapy; CGI-S=Clinical Global Impression Scale – Severity; COWS=clinical opiate withdrawal scale; C-SSRS=Columbia Suicide Severity Rating Scale; ECG=electrocardiogram.

^a Visits labeled “Phone” should occur by telephone whenever possible. In regions where local privacy restrictions do not permit contact by telephone, alternative forms of contact are acceptable

- ^b If any AEs are reported that relate to opioid withdrawal (eg, nausea, vomiting, restlessness, hyperhidrosis) during a phone assessment, the subject will be asked to come into the clinic as soon as possible to receive a COWS assessment
- ^c Any changes since last visit to be recorded
- ^d Possession of card to be confirmed at each clinic visit until Visit 18 when card should be collected
- ^e Via subject query
- ^f Vital sign measurements at all visits to include oral temperature, respiratory rate, blood pressure and heart rate. Respiratory rate, blood pressure and heart rate to be measured in the supine position
- ^g “Since Last Visit” version to be administered
- ^h Local drug screen via dipstick
- ⁱ COWS to be administered by a medical professional

8.3. Study Procedures Descriptions

8.3.1. Informed Consent

The nature of the study and its risks and benefits will be explained to the subject by the principal investigator or designated study personnel as outlined in [Section 17.3](#).

Prior to the administration of any study-specific procedures, authorized study personnel will obtain written informed consent from each potential subject.

8.3.2. Confirmation of Eligibility

For New Subjects, eligibility for participation in the study will be confirmed at the screening visit and reconfirmed at Visit 2 predose, on the first day of dosing.

Continuing Subjects and Lead-in Subjects will not attend a screening visit. Their eligibility will be confirmed at Visit 2. Identical assessments collected at Visit 2 for Lead-In Subjects (if performed) and the last treatment visit of the antecedent study for Continuing Subject their last visit of the antecedent ALKS 5461 study in which they participated will not be repeated at Visit 2 unless more than 10 days elapses between visits.

8.3.3. Demographics

For New Subjects only, demographic data will be reviewed and documented at screening.

For Continuing Subjects and Lead-in Subjects, demographic information will be carried over from information recorded in the antecedent ALKS 5461 study in which they participated.

8.3.4. Medical and Psychiatric History

For New Subjects, medical and psychiatric history will be reviewed and documented at screening. Information collected for psychiatric history should include duration of current MDE, number of lifetime MDEs, number of prior ADT failures and number of ADT failures within the current MDE. For all participating subjects, this information will be carried over from information recorded in the antecedent ALKS 5461 study in which they participated.

8.3.5. Physical Examination

For New Subjects, a full physical examination will be performed at screening. All participating subjects will have brief, symptom-directed physical examinations at all other time points specified in [Table 2](#) and [Table 3](#).

8.3.6. Height

For New Subjects only, height will be measured at the screening visit.

8.3.7. Weight

For New Subjects, weight will be measured at the screening visit. All participating subjects will be weighed at all other time points shown in [Table 2](#) and [Table 3](#).

Subjects should be weighed on the same scale for each measurement under the same conditions, with a consistent amount of clothing for each measurement. Subjects should remove shoes and all personal items prior to body weight measurement.

8.3.8. Vital Signs

Vital signs will be measured at each visit and include oral body temperature, respiratory rate, blood pressure, and heart rate. Blood pressure, respiratory rate and heart rate will be measured after the subject has been in a supine position for at least 5 minutes.

Effort will be made to measure all blood pressure and pulse rate from the same arm, preferably the subject's dominant arm, throughout the study.

The blood pressure cuff will be calibrated per study site standard procedures. Automated measurement is preferred, but if performed manually, heart rate will be measured in the brachial artery for at least 30 seconds.

As specified in [Table 2](#), on the first day of dosing, vital signs are to be measured predose.

8.3.9. 12-Lead Electrocardiogram

A 12-lead ECG will be conducted at the time points specified in [Table 2](#) and [Table 3](#). All scheduled ECGs must be performed after the subject has rested quietly for at least 5 minutes in the supine position.

ECGs will be conducted using calibrated equipment and assessed by a qualified clinician. The following ECG parameters will be collected: heart rate, RR, PR, QRS, and QT. QTcB (QT interval corrected using the Bazett formula), and QTcF will be automatically calculated by the ECG machine.

ECGs will be additionally evaluated by a central reader.

8.3.10. Concomitant Medication Review

At screening all New Subjects will be asked about the medications they have taken in the last 30 days. For a potential subject to qualify for the study, those exclusions outlined in [Section 8.4.2.2](#) must be ruled out. At each subsequent study visit, review of concomitant medications will be repeated for all participating subjects. Concomitant medications to be reviewed at each study visit include:

- prescription medications (including ADT)
- nonprescription/ over-the-counter (OTC) medications
- vitamins and supplements

The investigator will record the following data on all medications used by the subject, as applicable: name, dose, regimen, route of administration, start and stop dates, and the indication for use.

8.3.11. Illicit Substances Review

For New Subjects, all illicit substances consumed/used within 30 days will be reviewed and recorded at the screening visit, including name, amount, frequency and start and stop dates. Changes at each subsequent study visit will be recorded for all participating subjects.

8.3.12. Emergency Treatment Cards

An emergency treatment card will be distributed to each subject prior to first dosing. The card will indicate that the subject will be receiving BUP, a partial opioid receptor agonist, and samidorphan, an opioid receptor antagonist. The card will include the investigator's contact information, a suggested pain management plan, and information regarding opioid blockade and withdrawal. Subjects will be instructed to keep the emergency treatment card with them at all times. See [Table 2](#) and [Table 3](#) for details on card distribution, confirmation of possession, and collection.

8.3.13. Pharmacokinetic Assessments

Plasma samples for PK will be collected according to the schedule of events ([Table 2](#)), from consenting subjects enrolled in the US only.

The date and time of last dose of study drug as well as ADT, and the date and time of the PK blood draw will be recorded. Blood samples for these analyses will be stored at $-20^{\circ}\text{C}\pm 10^{\circ}\text{C}$.

Samples will be assayed by a central laboratory for determination of BUP and samidorphan concentrations, as well as relevant metabolites. Concentrations of background ADTs that subjects report taking during the study may be quantified, as appropriate.

8.3.14. Adverse Event Monitoring

The monitoring of adverse events will begin once informed consent is obtained and will be performed at each visit (see [Section 13](#)). Adverse events will be monitored continuously until the completion of the final study visit.

Adverse events and serious adverse events (SAEs) are defined in [Section 13.1](#) and [Section 13.2](#), respectively.

[Section 13.4](#) provides guidance on the monitoring and reporting requirements for adverse events. [Section 13.5](#) provides guidance on the reporting requirements for SAEs.

8.3.15. Laboratory Assessments

8.3.15.1. Serology Testing

New Subjects will provide a blood sample for a serology panel testing for hepatitis B surface antigen, anti-hepatitis C antibodies, and HIV at screening. Results must be negative for a subject to be eligible for the study.

8.3.15.2. Breath Alcohol Test

New subjects will undergo an alcohol test at screening via breathalyzer. A negative breath alcohol will be required for a New Subject to enter into the study. However, the test at Visit 1 may be repeated based on investigator judgment.

The breath alcohol test may be repeated for any participating subject at any time during the study, should the investigator feel it is warranted.

8.3.15.3. Urine Drug Screening

New Subjects will undergo urine drug screening for drugs of abuse at Visit 1 and laboratory analysis will be centralized. At all other time points specified in [Table 2](#) and [Table 3](#), all participating study subjects will have urine drug screening via dipstick; results will be analyzed by the local laboratory.

Drug screening will be performed for amphetamines, barbiturates, benzodiazepines, cocaine (metabolite), tetrahydrocannabinol, opioids, and phencyclidine. The opioid panel to be performed at screening for New Subjects (analyzed centrally) will include BUP, codeine, hydrocodone, hydromorphone, methadone, morphine, oxycodone, and oxymorphone. Drug screens administered at all other visits as specified in [Table 2](#) and [Table 3](#) (analyzed locally) will include all aforementioned opioids.

Negative urine drug screening at Visit 1 and Visit 2 will be required for a subject to enter in the study. However, an exception may be made for a benzodiazepine, when such medication is medically indicated for insomnia.

The urine drug test at screening may be repeated based on investigator judgment. The test can also be repeated at any time during the study, should the investigator feel it is warranted. Action taken in response to a positive urine drug screen after Visit 2 should be based on a medical evaluation in consultation with the medical monitor.

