9. TREATMENT OF SUBJECTS

9.1. Study Drug Dose and Administration

9.1.1. Description of ALKS 5461

The ALKS 5461 drug product will be formulated as tablets for sublingual (SL) administration and will contain a ratio of 1:1 BUP: samidorphan as free base equivalents by weight. BUP is a Schedule III narcotic and samidorphan is a Schedule II controlled substance. Thus, ALKS 5461 should be treated as a Schedule II controlled substance in the US. Outside the US, ALKS 5461 should be handled according to local regulations. See [Section 10](#) for information on storage and handling of controlled substances.

The study drug formulation contains common pharmaceutical excipients that are listed in the US as “GRAS” (Generally Recognized As Safe [GRAS]) and accepted for use as food additives in Europe: lactose monohydrate, microcrystalline cellulose, croscopvidone, sucralose, citric acid, sodium citrate, and magnesium stearate.

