- For the shifts from within normal reference limits / low to high: the numerator is defined as the number of subjects with a post-baseline results above the ULRR, and the denominator is defined as the number of subjects with a baseline value within the limits or below the LLRR.

Pregnancy and drug screening data will be listed. For urinalysis, rate of abnormalities at any post-baseline visit during treatment period will be summarized.

 Table 4:
 Potentially Clinically Significant Abnormal Laboratory Values

Category	Parameter	Criteria		
Hematology	Eosinophils	$>1.0x10^3/\mu L$		
	Hematocrit	≤32% and 3 point decrease from baseline (Female) ≤37% and 3 point decrease from baseline (Male)		
	Hemoglobin	≤9.5 g/dL (Female) ≤11.5 g/dL (Male)		
	Leukocytes	$\leq 2.8 \times 10^{3} / \mu L$ $\geq 16 \times 10^{3} / \mu L$		
	Neutrophils, Absolute	$<1.5x10^{3}/\mu L$		
	Platelets	$<75.1 \times 10^{3} / \mu L$ $\geq 700 \times 10^{3} / \mu L$		
Chemistry	Alanine Aminotransferase	≥3xULRR		
	Albumin	<2.5 g/dL		
	Alkaline Phosphatase	≥3xULRR		
	Aspartate Aminotransferase	≥3xULRR		
	Bicarbonate	<15 mmol/L >31 mmol/L		
	Blood Urea Nitrogen (BUN)	>30 mg/dL		
	Calcium	<8.2 mg/dL >12 mg/dL		
	Chloride	≤90 mmol/L ≥118 mmol/L		
	Creatine Phosphokinase	>3xULRR		
	Creatinine	≥2 mg/dL		

Table 4: Potentially Clinically Significant Abnormal Laboratory Values (Continued)

Category	Parameter	Criteria
	Gamma Glutamyltransferase	≥3xULRR
	Glucose	<50 mg/dL
		>200 mg/dL
	HDL Cholesterol	≤30 mg/dL
	Lactate Dehydrogenase	>3xULRR
	LDL Cholesterol	≥160 mg/dL
	Phosphate	<2 mg/dL >5 mg/dL
	Potassium	<3 mmol/L >5.5 mmol/L
	Prolactin	>1xULRR
	Sodium	<130 mmol/L >150 mmol/L
	Total Bilirubin	≥2 mg/dL
	Total Cholesterol	>300 mg/dL
	Triglycerides	≥120 mg/dL (Female) ≥160 mg/dL (Male)
	Uric Acid	>9 mg/dL >8 mg/dL (Female) >10 mg/dL (Male)
Urinalysis	Glucose Protein	at least 2+

Abbreviations: BUN=blood urea nitrogen; HDL=high density lipoproteins; LDL=low density lipoprotein; ULRR=upper limit of referene range

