APPENDIX 1. AESI – ABUSE POTENTIAL

Preferred Term	Adhoc SOC
Accidental overdose	AP_abuse behavior
Drug abuser	AP_abuse behavior
Drug diversion	AP_abuse behavior
Drug level above therapeutic	AP_abuse behavior
Drug level increased	AP_abuse behavior
Drug screen	AP_abuse behavior
Drug screen positive	AP_abuse behavior
Intentional overdose	AP_abuse behavior
Intentional product misuse	AP_abuse behavior
Intentional product use issue	AP_abuse behavior
Maternal use of illicit drugs	AP_abuse behavior
Needle track marks	AP_abuse behavior
Neonatal complications of substance abuse	AP_abuse behavior
Overdose	AP_abuse behavior
Prescription drug used without a prescription	AP_abuse behavior
Prescription form tampering	AP_abuse behavior
Product tampering	AP_abuse behavior
Substance abuse	AP_abuse behavior
Substance abuser	AP_abuse behavior
Substance use	AP_abuse behavior
Substance-induced mood disorder	AP_abuse behavior
Substance-induced psychotic disorder	AP_abuse behavior
Toxicity to various agents	AP_abuse behavior
Acute psychosis	AP_non-specific
Aggression	AP_non-specific
Cognitive disorder	AP_non-specific
Confusional state	AP_non-specific
Delirium	AP_non-specific
Delusional disorder, unspecified type	AP_non-specific
Depersonalisation/derealisation disorder	AP_non-specific
Disorientation	AP_non-specific
Dissociation	AP_non-specific
Disturbance in attention	AP_non-specific
Disturbance in social behaviour	AP_non-specific
Dizziness	AP_non-specific
Dopamine dysregulation syndrome	AP_non-specific
Emotional disorder	AP_non-specific
Flight of ideas	AP_non-specific
Medication overuse headache	AP_non-specific

Preferred Term	Adhoc SOC
Mental impairment	AP_non-specific
Mood altered	AP_non-specific
Mood swings	AP_non-specific
Narcotic bowel syndrome	AP_non-specific
Paranoia	AP_non-specific
Psychotic behaviour	AP_non-specific
Psychotic disorder	AP_non-specific
Sedation	AP_non-specific
Somnolence	AP_non-specific
Stupor	AP_non-specific
Euphoric mood	AP-euphoria related
Feeling abnormal	AP-euphoria related
Feeling drunk	AP-euphoria related
Feeling of relaxation	AP-euphoria related
Hallucination	AP-euphoria related
Hallucination, auditory	AP-euphoria related
Hallucination, gustatory	AP-euphoria related
Hallucination, mixed	AP-euphoria related
Hallucination, olfactory	AP-euphoria related
Hallucination, synaesthetic	AP-euphoria related
Hallucination, tactile	AP-euphoria related
Hallucination, visual	AP-euphoria related
Inappropriate affect	AP-euphoria related

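### The on-treatment urine screens test for buprenorphine, which the study drug contains, and neither document separates that expected positive from positives for other drugs

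*Protocol*

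**What the plan says.** **Panel.** Protocol 8.3.15.3 says the opioid part of the central screen "will include BUP, codeine, hydrocodone, hydromorphone, methadone, morphine, oxycodone, and oxymorphone". For the dipstick screens at all other scheduled time points, read locally, it says the panel "will include all aforementioned opioids". The panel also covers amphetamines, barbiturates, benzodiazepines, cocaine metabolite, tetrahydrocannabinol and phencyclidine.

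**Study drug.** Protocol 9.1.1 says the tablets "will contain a ratio of 1:1 BUP: samidorphan", and this holds at every dose level used.

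**Timing.** Protocol Table 2 schedules local screens on treatment at Visits 3, 8, 10, 12 and 14. Visit 14 is to fall within 24 hours of the last dose.

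**Handling of a positive.** For later screens, Protocol 8.3.15.3 has the medical monitor consulted and says "Action taken in response to a positive urine drug screen after Visit 2 should be based on a medical evaluation". No analyte is named. The only analyte exception in the protocol is a benzodiazepine medically indicated for insomnia, and it concerns entry to the study.

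**Analysis.** SAP 3.7.4.2 says "Pregnancy and drug screening data will be listed", and no summary table is planned. SAP Appendix 1 assigns the preferred terms Drug screen and "Drug screen positive" to the abuse-behavior category of the abuse-potential events of special interest (AESI), with no condition on analyte.

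**The concern.** Abuse potential is the first AESI listed in SAP 3.7.3, and Protocol Section 5 gives countering the abuse and dependence risk of BUP as the reason for including samidorphan. The urine screen is the scheduled laboratory check for drugs other than the study drug. PK assays cover only BUP, samidorphan, metabolites and background antidepressants, in consenting US subjects. The illicit-substances review relies on what the subject reports.

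One of the analytes on that screen is present in every tablet. Neither the protocol wording nor the SAP coding says which analyte makes a screen positive for this purpose. Two things are at stake:

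- Sites may handle the same expected BUP result differently. If some report it as an adverse event and others do not, the abuse-behavior count partly reflects reporting habit.
- A reader of the study report would find no rate of positives for drugs other than the study drug. Those results would sit in a listing among expected BUP positives.

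**Working it through.** The plan gives no figure for the drug screen, so there is none to reproduce. The check sets the texts side by side and then bounds how often the expected result would occur.

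**1. Text**

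| Question | Answer | Source |
|---|---|---|
| Is BUP on the local panel after the screening visit? | Yes | Protocol 8.3.15.3 |
| Does every study tablet contain BUP? | Yes | Protocol Section 5, 9.1.1 |
| Is a BUP-only positive exempted or explained? | No | Neither document |
| Does the protocol declare each positive an event? | No, it sets the basis for any action | Protocol 8.3.15.3 |
| What does the abuse-potential table count? | Reported treatment-emergent adverse events by preferred term | SAP 3.7.3 |
| When does a laboratory value become an adverse event? | When the investigator judges it clinically significant | Protocol 13.1 |
| Is any drug-screen summary planned? | No, listing only | SAP 3.7.4.2 |

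The panel has 1 + 7 = 8 opioids and six non-opioid classes. Only BUP is made uninformative by study-drug intake.

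**2. How often a BUP positive is expected**

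Let s be the chance of a BUP positive on one screen in a subject taking the tablet. The documents give no sensitivity or cutoff, so s is assumed over a wide range. For the five on-treatment screens, assumed independent, P(at least one BUP positive) = 1 − (1 − s)^5.

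| Assumed s | P(at least one in 5) |
|---|---|
| 0.10 | 1 − 0.90^5 = 41% |
| 0.30 | 1 − 0.70^5 = 83% |
| 0.50 | 1 − 0.50^5 = 97% |
| 0.80 | 1 − 0.20^5 = 99.97% |

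Imperfect adherence lowers s. With 70% recent intake and sensitivity 0.80 (both assumed), s = 0.70 × 0.80 = 0.56 and the result is 1 − 0.44^5 = 98%. Screens within one subject are probably positively correlated, which lowers these figures. With perfect correlation the probability equals s itself, so at s = 0.50 it lies between 50% and 97%. The four follow-up screens in Protocol Table 3 are not counted.

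**3. Why analyte matters**

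Suppose a screen counts as positive if any analyte is positive. Let t be the sensitivity for another drug that is being used, and b the background positivity for all analytes other than BUP. The per-screen likelihood ratio is

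[1 − (1 − s)(1 − b)(1 − t)] / [1 − (1 − s)(1 − b)].

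With b = 0.02 and t = 0.80 (assumed):

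- s = 0.50: 0.902 / 0.510 = 1.8
- s = 0.80: 0.961 / 0.804 = 1.2
- s = 0.95: 0.990 / 0.951 = 1.04
- BUP set aside: [1 − 0.98 × 0.20] / 0.02 = 0.804 / 0.02 = 40

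With t = 0.95 the last figure is 0.951 / 0.02, or about 48. The same dipsticks are nearly uninformative when analytes are pooled and highly informative when they are not.

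**The case against.** The case on the other side is strong on several points.

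- **A reader might infer that the screens cannot detect abuse.** The documents do not support that. Seven other opioids and six non-opioid classes remain on the panel, and nothing suggests that study drug turns them positive. Only the BUP result, or a pooled reading, is uninformative.
- **A reader might infer that nearly every adherent subject will be counted as showing abuse behavior.** The documents do not support that either. SAP 3.7.3 counts reported adverse events, not raw dipsticks, and Protocol 13.1 makes a laboratory value an adverse event only on the investigator's judgment. SAP 3.7.2 carries verbatim terms into the adverse event listings. SAP 3.7.3 adds supportive AESI listings, and narratives for clinically meaningful events.
- **The protocol sentence leaves room for judgment.** It bases any action on a medical evaluation with the medical monitor, and both parties know that the subject takes BUP. This stands for individual handling. It does not define a positive for analysis.
- **The frequencies rest on assumptions.** This stands. At s = 0.10 most subjects would have no BUP positive in five screens.
- **The screen is not the only abuse-related check.** This also stands: pill counts, drug accountability and the illicit-substances review are scheduled too. None of them is a laboratory test for other drugs.
- **Listing the data is a legitimate choice in a descriptive safety study.** In general it is. It serves less well where one analyte is expected to be positive by design.

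That sites would dismiss a codeine or oxycodone positive as expected is conjecture. No text suggests it.

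**Conclusion.** The point holds in a limited form. During treatment a BUP positive marks exposure and carries no information on abuse, because the dipstick cannot tell study drug from any other BUP. Neither the post-Visit 2 wording nor the Appendix 1 mapping separates it from positives for other drugs, and no summary of those other positives is planned.

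The consequence is possible misclassification in the abuse-potential table that depends on site reporting, and a missing descriptive result. How many reports would be misclassified cannot be estimated, because the documents do not indicate how often sites would report a BUP-only positive as an adverse event. The range of 41% to over 99.9% is the chance that a subject has at least one BUP-positive dipstick. It is not a count of abuse events, and it rests on assumed sensitivities from 0.10 upward and on independent screens.

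The change is worth making because abuse potential is a named special interest and the correction is mostly wording. The point concerns screens after Visit 2 only, not eligibility at Visit 2.

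**What to change.** 1. **SAP 3.7.4.2.** Add one descriptive table of screens after Visit 2, by visit, by prior ALKS 5461 exposure and overall. Give the number and percentage positive for each analyte, and for at least one analyte other than BUP and other than a permitted benzodiazepine. Put BUP in a separate row, labelled as a marker of exposure.
2. **SAP Appendix 1.** State that a reported Drug screen or Drug screen positive event is not counted under abuse behavior when BUP is the only positive analyte during study-drug exposure.
3. **Protocol 8.3.15.3.** Reconcile the presence of BUP on the local panel, and the undefined positive screen after Visit 2, with the BUP content of the study drug. This concerns what counts as a positive, not what clinical action follows.

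The cost is one table and a few lines of text, with no new visits or samples. For scale, if background positivity for the other analytes were 1%, 2% or 5% per screen (assumed, independent screens), 1 − (1 − b)^5 gives 4.9%, 9.6% or 22.6% of subjects with at least one non-BUP positive in five screens.

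There are two limits. Non-study BUP use on treatment would not be counted, but the dipstick cannot identify it in any case. The sponsor must also confirm that dipstick results are recorded by analyte. If the local test gives only one pooled opioid result, the opioid rows cannot be built from it, and only the non-opioid classes could be tabulated.
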